2.3 Design Summary

This is a randomized clinical trial, comparing the frequency of identification of abnormal growth and / or amniotic fluid among low risk women who either have serial USE vs. those who have clinically indicated USE. Women will be randomized to one of two groups:

- Group 1: routine third trimester care with clinically-indicated ultrasound (control)
- Group 2: ultrasound evaluation for fetal growth and amniotic fluid every 4 weeks starting at 30 weeks (intervention group). Thus, if they continue to term, there will be 3 additional ultrasounds exams (30, 34 and 38 weeks).

Eligible subjects who meet inclusion/exclusion criteria will be randomized in a 1:1 ratio using permuted block randomization in order to prevent imbalances between groups.

2.4 Sample Size Calculation

The definition of the primary outcome is presence of SGA (EFW<10%), LGA (EFW>10%), oligohydramnios, or polyhydramnios and is not based on any outcomes after birth.

The estimate for the primary outcome is based on the following assumptions:

- In uncomplicated pregnancies, the likelihood of identifying abnormal growth or amniotic fluid is 10% in the control group.
- In the intervention group, we hypothesize the likelihood of detecting abnormal condition to be 25%.
- To detect an increase in the primary outcome from 10% in control to 25% in the intervention group with 80% power and alpha of 0.05, a total of 194 (97 in each arm) women need to be randomized.
- We estimate that 5% of patients will be lost to follow up based on a previous pilot study (21). The total sample size will be 206 women (103 /group) to allow for loss to follow-up.

2.5 Eligibility Criteria

2.5.1 Inclusion Criteria

- 1. Maternal age of 18 at the time of consent
- 2. Singleton gestation

2.5.2 Exclusion Criteria

- 1. First sonographic examination after 20 weeks
- 2. Women with any of the following co-morbidities:
 - Autoimmune disorders (antiphospholipid antibody, lupus, rheumatoid arthritis, scleroderma)
 - b. Cerclage in the index pregnancy
 - c. Diabetes mellitus-gestational or pre-gestational
 - d. Hematologic disorders (coagulation defects, sickle cell disease, thrombocytopenia, thrombophilia)
 - e. Hypertension (chronic or pregnancy induced) before enrollment
 - f. HIV (human immunodeficiency virus)
 - g. Institutionalized individuals (prisoners)
 - h. Prior obstetric history of: 1) intrauterine growth restriction, 2) preterm birth before 34 weeks, 3) severe preeclampsia, eclampsia, HELLP syndrome, and 4) stillbirth after 24 weeks or neonatal death
 - i. Preterm labor or ruptured membranes before enrollment
 - j. Psychiatric disorder (bipolar, depression) on medication
 - k. Placenta previa / 3rd trimester bleeding
 - I. Renal insufficiency (serum creatinine > 1.5 mg/dL)
 - m.Restrictive lung disease
 - n. Fetal red blood cell isoimmunization
 - o. Seizure disorder on medication
 - p. Thyroid disease on medication
 - q. Body Mass Index (BMI) above 40 kg/m²
- **3.** Major fetal Anomaly including: anencephaly, spina bifida, bilateral renal agenesis, cystic hygroma with hydrops, diaphragmatic hernia, or congenital heart defects

4. Unable to understand consent in English or Spanish

2.5 Informed Consent Criteria

Written informed consent must be obtained before entry into the study. Full disclosure of the nature and potential risks of participating in the trial is to be made. A copy of the signed consent form for the study will be provided to the patient.

Women randomized to the intervention group will not be charged for ultrasound exams which are part of the study design. The departmental funds will pay for these exams. If ultrasound abnormalities are noted (e.g. abnormality of the fluid or growth) subsequent ultrasound exams are needed, according to American College of Obstetricians and Gynecology (ACOG) guidelines (Table 3). For these indicated ultrasound exams the insurance company will be billed and these exams are not covered by the departmental funds.

Among women in the control arm, the ultrasound exams will be done only when indicated according to the ACOG guidelines. Some of the common indications for USE include: 1) difference in GA and fundal height > 3 cm; 2) new onset hypertension; 3) decreased fetal movement; 4) spotting/ bleeding; 5) preterm premature rupture of membranes, 6) preterm labor; 7) maternal trauma. Since these exams are indicated, the charges will be submitted to the appropriate insurance company.

3.1 Methods

After gestational diabetes is ruled out, usually by 28-30 weeks, and the woman is confirmed to meet the eligibility criteria, she will be approached for participation. Patients will be randomized using the random permuted block randomization method using allocation tables created by a statistician. The sonographic examination will be done by a registered diagnostic medical sonographer (RDMS).

The examinations will be done after the prenatal visits and there will be no charges for the ultrasound. No economic burden will be imposed on participants. Consistent with the ACOG recommendations that the sonographic exams be repeated every 4 weeks, we will repeat the exams every 4 weeks. Thus, if a women is recruited at 30 weeks, she will have sonographic examination at 30, 34 and at 38 weeks. If a woman develops obstetric complications, such as preterm labor or hypertensive disease of pregnancy, which requires sonographic examination

she will have exams by RDMS but based on intent-to-treat principle continue to be in the group she is randomized to. Clinicians managing the women will be informed of the findings of the USE.

The third trimester ultrasounds will follow the American Institute of Ultrasound in Medicine (2007) guidelines. In particular, biparietal diameter (BPD) will be measured at the level of thalami and insula, and measurement taken from outer edge of the proximal skull to the inner edge of the distal skull. The head circumference (HC) will be measured at the same level as the biparietal diameter, around the outer perimeter of the calvaria. Since HC is not affected by head shape, it will be used if the head is flattened (dolichocephaly) or rounded (brachycephaly). Abdominal circumference (AC) measurement will be determined at the skin line on a true transverse view at the level of the junction of the umbilical vein, portal sinus and the fetal stomach. Femoral length (FL) will be measured with the beam of insonation being perpendicular to the shaft, excluding the distal femoral epiphysis (Chervenak 1998, ACOG 2009). Estimated fetal weight will be derived using the regression equation proposed by Hadlock (1985): Log_{10} (EFW) = $1.5662 - 0.0108(HC) + 0.0034(HC)^2 + 0.0468(AC)+0.171(FL)-0.003685(AC)(FL) with EFW being estimated fetal weight; HC, head circumference; AC, abdominal circumference, and; FL, femur length. If a fetal anomaly which was not noted in early survey is discovered during the <math>3^{rd}$ trimester USE, clinicians and women be informed.

Abnormalities of fetal growth are fetal growth restriction (FGR) and large for gestational age (LGA). A fetus will be considered to have FGR if the estimated fetal weight is < 10% for gestational age and LGA if the estimate is > 90% for gestational age. Amniotic fluid will be estimated using single sonographic deepest pocket (SDP), which involves finding and vertically measuring the largest cord-free pocket of amniotic fluid or will be calculated by the sum of the maximum vertical pockets in all 4 quadrants. Oligohydramnios, or decreased amniotic volume, is a SDP less than 2 cm or amniotic fluid index < 5.0 cm; hydramnios, or excessive amniotic fluid, is a SDP >8 cm or amniotic fluid > 24.0 cm(ACOG 2009).

3.2 Baseline Procedures

In addition to information for eligibility, project gestational age, the following variables will be collected from the patient's chart.

- Demographics (maternal age, race, ethnicity)
- Medical history (obstetrical history, body mass index pre-pregnancy and at delivery, maternal comorbidities)
- Ultrasound information (fetal growth and amniotic fluid measurements)
- Delivery characteristics
- Timing of delivery
- Neonatal outcomes while hospitalized

3.3 Patient Management

Clinicians managing these women will be informed of the sonographic findings if any of the following is noted: 1) FGR or estimated fetal weight < 10% for gestational age, 2) LGA or estimated fetal weight > 90% for gestational age, 3) oligohydramnios, 4) hydramnios, or 5) sonographic findings which influences clinical management e.g. spontaneous bradycardia or previously undetected fetal anomaly. Women with abnormal findings will be notified. They will also be informed that their clinicians are aware and management will be according to guidelines and departmental practices (Table 3).

Abnormalities seen on Ultrasound	Recommendation to Clinicians
FGR (estimated fetal weight < 10% for GA)—from ACOG Practice Bulletin # 134 (reference 7)	 Unless previously done, perform a detailed fetal anatomic survey Serial ultrasound evaluations of the following: (1) Fetal growth with Doppler velocimetry (every 3- 4 weeks) (2) Biophysical profile with or without non-stress test (weekly) along with umbilical artery Dopplers One course of antenatal corticosteroids between 24 and 34 weeks of gestation in the week before delivery is expected Delivery at 38-39 weeks or sooner if abnormal results of antepartum testing or co-
LGA (estimated fetal weight)— from ACOG Practice Bulletin # 22 (reference 22)	 If EFW is ≥ 5,000 in non-diabetic, recommend primary cesarean delivery
 Oligohydramnios—from ACOG Practice Bulletin # 145 (reference 2) 	 Consider a repeat fetal structural survey to rule out possible missed a fetal malformation Non-stress test (NST) and AFI (or biophysical profile) once or twice weekly until delivery For women with idiopathic oligohydramnios, we suggest delivery at 36 to 37 completed weeks of gestation rather than expectant management
Polyhdyramnios—(reference 23)	 A repeat comprehensive sonographic evaluation is recommended to determine whether fetal anomalies or fetal hydrops is present. Suggested laboratory evaluations depend upon

Table 3. Abnormal findings and recommendation to clinicians

Abnormalities seen on	Recommendation to Clinicians	
Ultrasound		
	 sonographic findings and may include testing for karyotype analysis, fetomaternal hemorrhage if fetal anemia is suspected, maternal serology to determine exposure to infectious agents (eg, syphilis, parvovirus, cytomegalovirus, toxoplasmosis, rubella), and appropriate tests for hereditary anemias (eg, alpha thalassemia) or metabolic abnormalities. We suggest treatment for polyhydramnios in singleton pregnancy only if there is preterm labor or significant maternal discomfort with amnioreduction. 	
Undetected fetal anomaly	 A repeat detailed sonographic evaluation Recommend offering karyotype analysis in if knowledge of the karyotype will affect management 	
Spontaneous Bradycardia	 Prolonged fetal monitoring on labor and delivery triage unit 	

3.4 Study Outcome Measures and Ascertainments

3.4.1 Primary outcome:

The primary outcome is presence of SGA (EFW<10%), LGA (EFW>10%), oligohydramnios, or polyhydramnios among uncomplicated pregnancies that have indicated versus serial USE starting at 30 weeks or more. These parameters are not based on any outcomes after birth.

3.4.2 Secondary outcomes:

- Composite Neonatal Morbidity (CNM) among the two groups
- Composite Maternal Morbidity (CMM) among the two groups.

3.4.3 Statistical Analysis

Intention to treat analyses will be performed. The rate of the primary outcome, abnormal fetal condition (estimated fetal weight < 10% or > 90% for GA, oligohydramnios or polyhydramnios), will be compared between the intervention and control group using a log binomial (or Poisson in case of nonconvergence) model with treatment group as a covariate to estimate relative risk and 95% confidence interval (CI). The definition of the primary outcome is presence of FGR (EFW<10%), LGA (EFW>90%), oligohydramnios, or polyhydramnios and is not based on any outcomes after birth. Therefore there is no issue about false-positives or false-negatives.

Each secondary outcome will be analyzed similarly. Based on the MFMU Network data that stated CNM occurs in 1.9% of women with uncomplicated pregnancies, we estimate that over 29,000 women need to be randomized to show one-third improvement in CNM (power 90%) among uncomplicated women that have routine ultrasound exams vs. those that have indicated ultrasound examinations. Hence our purpose for these outcomes is to calculate unbiased estimates to provide information for the large multicenter trial in MFMU Network.

We will also conduct a Bayesian analysis of the primary outcome to calculate probability of treatment benefit or harm. We will use a neutral prior distribution for the intervention effect that excludes implausible large treatment effects: Normal (0, SD=0.70) in the log RR scale (prior 95% interval for the RR of 0.23-4.35) (28) Point estimates of treatment effect and 95% credible intervals will be reported with posterior probabilities of benefit and/or harm.

4 Ethics

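### The Bayesian prior is stated inconsistently: an SD of 0.70 on the log RR scale gives a 95% interval of 0.25 to 3.94, whereas the printed 0.23 to 4.35 needs an SD of 0.75

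*Combined protocol and SAP*

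**What the plan says.** Section 3.4.3 (Statistical Analysis) first sets out a log-binomial model, or Poisson if that fails to converge, to compare the primary outcome between arms. It then adds a second analysis of the same outcome: "We will also conduct a Bayesian analysis of the primary outcome to calculate probability of treatment benefit or harm".

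The prior is described in words, "We will use a neutral prior distribution for the intervention effect that excludes implausible large treatment effects", and then in numbers, with the distribution followed by its interval in parentheses: "Normal (0, SD=0.70) in the log RR scale (prior 95% interval for the RR of 0.23-4.35". The section also commits to reporting point estimates, 95% credible intervals and posterior probabilities of benefit or harm.

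The SD and the interval appear nowhere else in the document. A literature citation follows the interval, but the cited paper is not part of the material under review.

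**The concern.** An SD and a 95% interval for a normal prior centred at zero carry the same information, since either one determines the other. Here they determine different priors.

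This matters for two reasons. First, the prior is an input that must be fixed before the data are seen, and as written the section supports two values. Second, the interval is what most readers will use to judge whether the prior really rules out implausibly large effects. If the SD is right, that interval is wrong, and the prior is somewhat more sceptical than it is said to be. If the interval is right, the analysis as specified would use the wrong SD.

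**Working it through.** **Inputs**

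- Prior mean 0 and SD 0.70 on the log RR scale; stated 95% interval 0.23 to 4.35 (section 3.4.3).
- Planning rates of 10% (control) and 25% (intervention); 97 women per arm before, and 103 after, the allowance for loss to follow-up (section 2.4). These are used only to gauge the effect.

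**Step 1. Interval implied by the stated SD.** The 95% interval is exp(0 ± 1.96 × SD).

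- SD 0.70: 1.96 × 0.70 = 1.372, so the limits are exp(−1.372) = 0.254 and exp(1.372) = 3.943, or 0.25 to 3.94. The printed interval is not reproduced.

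**Step 2. SD implied by the stated interval.** SD = |ln(limit)| / 1.96.

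- Upper limit: ln(4.35) / 1.96 = 0.750.
- Lower limit: −ln(0.23) / 1.96 = 0.750.
- Check: exp(±1.96 × 0.75) = 0.230 and 4.349, which match the printed 0.23 and 4.35 to two decimals.

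The two limits agree with each other and both point to 0.75.

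**Step 3. Could another reading reconcile them?**

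| Reading of 0.70 | Resulting interval or limit |
|---|---|
| SD rounded from between 0.695 and 0.705 | upper limit about 3.90 to 3.98 |
| Multiplier 2 instead of 1.96 | 0.25 to 4.06 |
| 0.70 is a variance | 0.19 to 5.15 |
| 0.70 is a precision | 0.10 to 10.41 |
| 96% interval | 0.24 to 4.21 |
| 97% interval | 0.22 to 4.57 |

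None gives 0.23 to 4.35. Working backwards, an upper limit that rounds to 4.35 requires an SD between 0.7495 and 0.7507. Under SD 0.70 the printed range would be about a 96.4% interval, but the text calls it 95%.

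**Step 4. Effect on the posterior (illustration).** Assume that the observed rates equal the planning rates, and use a normal likelihood for the log RR.

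- Observed log RR: y = ln(0.25 / 0.10) = ln(2.5) = 0.916.
- Its variance with 97 per arm: v = (0.90/0.10 + 0.75/0.25) / 97 = 12 / 97 = 0.1237, so SE = 0.352.
- Posterior mean = y × SD² / (SD² + v); posterior variance = SD² × v / (SD² + v).
- SD 0.70 (variance 0.49): mean = 0.916 × 0.49 / 0.6137 = 0.732; variance = 0.0988.
- SD 0.75 (variance 0.5625): mean = 0.916 × 0.5625 / 0.6862 = 0.751; variance = 0.1014.

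| Women per arm | Prior SD | Posterior RR (95% credible interval) | P(RR > 1) |
|---|---|---|---|
| 97 | 0.70 | 2.08 (1.12 to 3.85) | 0.990 |
| 97 | 0.75 | 2.12 (1.14 to 3.96) | 0.991 |
| 103 | 0.70 | 2.10 (1.15 to 3.83) | 0.9921 |
| 103 | 0.75 | 2.14 (1.16 to 3.93) | 0.9927 |

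The prior variances differ by about 15% (0.5625 / 0.49 = 1.148), but at the planning rates the data dominate both.

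**The case against.** The arithmetic is hard to dispute. The better argument is that the discrepancy hardly matters. The Bayesian analysis is additional to the log-binomial comparison, the sample size does not use the prior, and the plan sets no posterior threshold, stopping rule or success criterion that could turn on the SD. At the planning rates the probability of benefit moves by about 0.001. It can also be said that the text names an explicit parameter and the interval only describes it, so an analyst would naturally code 0.70 and the fault shrinks to a wrong parenthesis.

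The first part stands. No decision in the plan changes with the choice of SD, and an analyst would gain almost nothing by switching.

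The second part stands only partly. Coding the printed SD is the natural default, but both limits match 0.75 to two decimals. The interval therefore looks like one calculated from a different SD, and it may be the figure that was intended. The document does not settle this. The cited paper might, but that cannot be assumed here.

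**Conclusion.** The inconsistency is real and can be confirmed from a single sentence of section 3.4.3. SD 0.70 and the interval 0.23 to 4.35 cannot both describe the same 95% prior. If SD 0.70 is intended, the printed upper limit is too high by 4.35 − 3.94 = 0.41 RR units. If the interval is intended, the SD should be 0.75.

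The expected effect on results is small: about 0.04 in the posterior RR, about 0.1 in the upper credible limit, and about 0.001 in the probability that the RR exceeds 1. These sizes rest on the planning rates, the planned numbers per arm, a normal approximation, and reading benefit as an RR above 1. The contradiction itself needs none of those assumptions.

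It is still worth correcting, because the prior is a prespecified input to a planned analysis of the primary outcome, and the differences appear at the precision normally reported.

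**What to change.** State one prior in section 3.4.3, with an SD and interval that agree. Two consistent pairs are available:

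- SD 0.70 with a 95% interval for the RR of 0.25 to 3.94; or
- SD 0.75 with a 95% interval for the RR of 0.23 to 4.35.

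The sponsor's statistician should confirm which was meant, and the choice should be recorded and locked before any outcome data are reviewed. If outcome data have already been seen, say so and report the analysis under both SDs.

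The cost is a correction to the SD or to its printed interval in the SAP. Sample size, consent and trial conduct are unaffected.

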4.1 IRB approval

IRB approval will be obtained through the Committee for Protection of Human Subjects (CPHS) prior to initiation of the study.

4.2 Consent process

We will have patients sign an informed written consent at the beginning of the study.

4.3 PHI

The MRN of the mother and the newborn will be kept on a separate list paired with a study ID number. The MRN will be maintained to track neonatal outcomes, which will not be readily available at the time of delivery. This database will be password protected and located on a folder within the UT server which will only be accessed by the principal investigator.

4.4 Data Handling and Record Keeping

The data for this study will be recorded on a spreadsheet that will be stored on computers in the medical school which are password protected and located in a locked office. A master list containing study ID linked with MRN will be maintained on these same computers. The MRN will be stored solely to track neonatal outcomes. The list will be discarded at the end of the study.

5 Quality Assurances

5.1 Data collection

Data will be collected on premade data sheets (see attachment) by either the principal investigators or Maternal-Fetal Medicine fellows.

